The image consists of a series of horizontal bars of varying lengths, rendered in black on a white background. The bars are arranged in a descending order of length from top to bottom. On the far left, there is a vertical dashed line. To the right of the dashed line, the first bar is white, followed by a black bar of moderate length. This pattern repeats several times, with a longer white bar preceding a very long black bar. The bars are separated by small gaps.

The image consists of a series of horizontal black bars of varying lengths and positions, set against a white background. The bars are irregular in shape, with some having sharp ends and others being more rounded. They are positioned in a way that suggests they are redacting text or obscuring specific information. The overall effect is one of a heavily redacted or abstracted document page.

A high-resolution grayscale image of a human face, likely a portrait. The image is framed by a thick black rectangular border. The face is centered and clearly visible against a white background. The skin tone is a light gray, with darker shadows on the left side and highlights on the right, giving it a three-dimensional appearance. The features, including the eyes, nose, and mouth, are well-defined.

A 4x4 grid of 16 black bars of varying lengths, representing data values. The bars are arranged in four rows and four columns. The first row has bars of length 1, 2, 4, and 8. The second row has bars of length 1, 2, 4, and 8. The third row has bars of length 1, 2, 4, and 8. The fourth row has bars of length 1, 2, 4, and 8.

 CONFIDENTIAL	Protocol No. GDX-44-008 Version No.4.0 including amendments 1 and 2 12 December 2017	Page 22 / 64
---	--	--------------

1. INTRODUCTION AND STUDY RATIONALE

Hepatocellular carcinoma (HCC) is the fifth most common malignancy worldwide in men (554,000 new cases in 2012) and the ninth in women (228,000 new cases in 2012) and the second cause of cancer death responsible for more than 746,000 deaths in 2012 (1).

The dual arterial-portal blood supply is one specific complexity for the hepatic vascularization. The liver has a unique dual blood supply, with a compensatory relationship existing between the two sources so that the arterial flow increases when the portal venous flow decreases. HCC are highly vascular tumors and derive neovasculature through the process of angiogenesis. Multiphasic contrast enhanced computed tomography scan (CT), magnetic resonance imaging (MRI) or ultrasound (US) allow evaluation of the liver during both the arterial and the portal venous phases of contrast enhancement and therefore have become important modalities for the detection and characterization of HCC.

Surveillance program have changed the spectrum of HCC by depicting more small HCCs than before. For example, in Japan, HCC less than 2cm represented 4.6% of the cases between 1976 and 1985 and 33.1% between 1996 and 2000 (2). Diagnosis of small HCCs is more difficult because they are less typical and may mimic benign lesions (3). On the contrary to lesions more than 3 cm, the specificity of diagnosing small HCC raises imaging specificity issues because of false positive cases corresponding to arterio-venous shunts, benign lesions or to other nodules (4). Dynamic characteristics with high intensity at arterial phase accompanied by a wash-out at portal or delayed phase are considered highly specific for HCC (5).

[figure not shown]
Gadolinium-Based Contrast Agents (GBCAs) have been used extensively in a large range of indications in MRI examinations. GBCAs consist of the active substance gadolinium (Gd) and a chelating agent. They can be categorized by their chemical structures into linear and macrocyclic agents and further subdivided by their charge (ionic or non-ionic). *In vitro* experiments have shown that the macrocyclic compounds are the most stable, with an undetectable release of Gd³⁺ ions under physiological conditions.

For multiphasic MRI, GBCA were found to participate to the characterization of malignancy of nodules in the liver. Extracellular GBCA are used for their ability to show typical characteristics for HCC with 0.820 (95% CI 0.776, 0.857) of sensitivity in patients with any-sized lesions; and estimated specificities were 0.934 (95% CI 0.881, 0.964) according to a recent meta-analysis (6).

P03277 is a new chemical entity discovered and developed by Guerbet. It is a non-ionic macrocyclic gadolinium (Gd) complex intended to be used in human, by intravenous administration, as a contrast agent for MRI.

P03277 has a molecular weight of 970.11 g/mol. [REDACTED]

[REDACTED] P03277 is used as an aqueous injectable solution for injection at a concentration of 0.5 M.

The ability of P03277 to be a MR contrast agent has been demonstrated by at least two-fold higher T1 relaxivity compared to other available GBCAs. A proof of concept has been obtained for the efficacy of P03277 as a MR contrast agent for CNS imaging in a model of brain tumor (C6 glioma) implanted in rats. In this experimental brain tumor model, the dose of 0.1 mmol/kg of P03277 allowed for an increase in contrast enhancement of at least 30% as compared to other GBCAs administered at dose of 0.1 mmol/kg, including MultiHance® (highest relaxivity among the GBCA).

P03277 is a Gd chelate with a very high stability, limiting the risk of release of toxic free Gd in the body. The results of preclinical data indicate a good tolerance and a low toxicity profile at dose levels and exposure much higher than the anticipated clinical dose. This satisfactory tolerance has been confirmed in a phase I/IIa study. In this study, 36 healthy volunteers and 12 patients were administered with a single dose of P03277 and 18 volunteers with placebo. No serious adverse reaction occurred in any of these volunteers at any of tested dose at 0.025, 0.5, 0.75, 0.1, 0.2, and 0.3 mmol/kg BW. No clinically significant changes in vital signs or laboratory findings were noted.

In this phase I/IIa study, pharmacokinetics profile was shown to be dose-dependent (linear) that is the reason why only one dose is considered as needed for this new proof of concept study. [REDACTED]

[REDACTED]

The aim of GDX-44-008 study is to explore the diagnostic value for HCC of P03277 triphasic imaging of suspected nodules in patients with liver diseases. Some small HCC usually showing atypical features may be better seen and characterized under imaging with P03277. Participating subjects will not directly benefit from P03277 MRI. They will be diagnosed according to a combination of examinations for standard of reference including imaging and/or histology analysis

Guerbet  CONFIDENTIAL	Protocol No. GDX-44-008 Version No.4.0 including amendments 1 and 2 12 December 2017	Page 24 / 64
--	--	--------------

2. STUDY OBJECTIVES

2.1 Primary Objective

To evaluate the diagnostic value (specificity and sensitivity) for hepatocellular carcinoma of P03277 in patients with suspected small nodules and chronic liver disease.

2.2 Secondary Objectives

To evaluate multiple quantitative and qualitative efficacy parameters and the safety (clinical and biological) profile of P03277 following single administration in suspected HCC patients

2.3 Sub-Study / Ancillary Study Objectives

Not applicable

 CONFIDENTIAL	Protocol No. GDX-44-008 Version No.4.0 including amendments 1 and 2 12 December 2017	Page 25 / 64
---	--	--------------

3. STUDY DESIGN

3.1 Protocol Description

Dual center, exploratory, non randomized, open label, two cohorts, two doses, phase IIa study.

The standard of reference for diagnostic will be given by the site according to their standard of care and adapted from EASL/EORTC diagnostic criteria (7) and considering previous contrast enhanced imaging (CT and/or MRI) and/or biopsy specimen analysis given on-site and/or the more recent AFP results available.

3.2 Study Duration

Subject participation duration could be from 2 days up to 3 months approximately

- The maximal period between subject screening and P03277 administration in the trial is 7 days but can be the same day if eGFR measurement within the last 7 days is available.
- Subject inclusion will be confirmed the day of administration with P03277 according to the eGFR results and urinary pregnancy test if applicable
- Subject will be followed up at +1 day safety visit
- Optionally and according to standard of care for histology analysis locally, the subject will have a specific biopsy or a surgically resected specimen collected at the time of loco-regional treatment. This procedure, whatever the type (biopsy or surgery), should be done between 3 days after P03277 administration and 13 weeks maximum. Alternatively it is acceptable to record results from histology done within 2 months prior to P03277 administration.

The study will be considered as completed once all the images collected for all the subjects will have been reviewed by expert readers.

3.3 Interim Analysis

Not applicable

3.4 Study Committee(s)

Not applicable

 CONFIDENTIAL	Protocol No. GDX-44-008 Version No.4.0 including amendments 1 and 2 12 December 2017	Page 26 / 64
--	--	--------------

4. SUBJECT SELECTION

4.1 Inclusion Criteria

1. Female or male adult subject aged at least 18 years old or older (subject having reached legal majority age).
2. Subject able and willing to participate to the study.
3. Subject having read the information and having provided his/her consent to participate in writing by dating and signing the informed consent prior to any study related procedure being conducted.
4. Subject presenting with liver cirrhosis or chronic liver disease as shown by previous liver biopsy or by combination of clinical, endoscopic, biological, ultrasound parameters, and elastography
5. Subject presenting with one to a maximum of 3 untreated hepatic nodule(s) of less than or equal to 3 cm (long axis) previously identified and/or characterized through enhanced CT and/or MRI within a maximum of 21 days before P03277 imaging, confirmed for HCC or not
6. Female subject must be using a medically approved contraception method* detailed below or be surgically sterilized or post-menopausal (>12 months amenorrhea)

**medically approved contraception methods include: female sterilization, barrier methods of contraception (condom or occlusive cap (diaphragm or cervical/vault caps) with spermicidal foam/film/cream/ vaginal suppository), use of oral, injected or implanted hormonal methods of contraception or other forms of hormonal contraception that have comparable efficacy (failure rate <1%), for example hormone vaginal ring or transdermal hormone contraception, placement of an Intrauterine Device (IUD) or Intrauterine System (IUS).*

7. Subject affiliated to national health insurance according to local regulatory requirement

To be selected and included in the study, the subject must meet all these inclusion criteria.

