7.1 Primary Criterion

For evaluation of **diagnostic value (defined as Sensitivity and Specificity) of P03277 for HCC** the following will be assessed:

Primary criteria:

- **Nodule diagnosis at P03277 imaging** (HCC, not HCC specify) will be assessed:
 - on a maximum of 3 hepatic nodules per subject
 - Based on visual qualitative analysis of P03277 triphasic imaging (arterial, portal and delayed phases) showing HCC typical hallmarks according to EASL/EORTC criteria (arterial hypervascularization and portal wash-out or delayed wash-out)
 - by two expert readers. In case of discordance, a consensus diagnostic will be obtained
- **The standard of reference** for diagnosing liver nodules (HCC, other malignant, regenerative or dysplastic nodule, benign, uncertain) will be given by the site according to their standard of care and according to adapted EASL/EORTC diagnostic criteria, considering previous contrast enhanced imaging (CT and/or MRI) and/or histology analysis and/or the more recent AFP results available:

HCC will be considered when:

- Histology is positive for HCC
- Or Nodule identified and characterized by typical features using two different triphasic contrast enhanced modalities. Typical features are arterial hypervascularization and portal wash-out or delayed wash-out

 CONFIDENTIAL	Protocol No. GDX-44-008 Version No.4.0 including amendments 1 and 2 12 December 2017	Page 33 / 64
---	--	--------------

- Or AFP>200ng/mL in a presence of a single nodule
 Other diagnosis than HCC could be based on imaging only and/or histology.

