9.1.4 Visit 4 – Optional (from 3 days up to 13 weeks)

Optionally, a biopsy will be done or surgically resected specimen will be collected at the time of loco-regional treatment and be analyzed for histology by local pathologist.

This procedure, whatever the type (biopsy or surgery), should be done between 3 days after P03277 administration to up to 13 weeks maximum. Alternatively it is acceptable to record results from histology done within 2 months prior to P03277 administration.

- **Examination results available for standard of reference diagnosis evaluation**
 - Date of nodule material collection (2 dates maximum)
 - Histological diagnosis per nodule : HCC, other malignant, regenerative or dysplastic nodule, benign, uncertain
- **Assessment of AEs that the investigator considers related to P03277 and/or study procedures.**

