12.3 Efficacy Data

Efficacy data will be summarized and presented by dose using the FAS and PP set for primary efficacy analysis and only using FAS for any other efficacy analysis.

Primary efficacy analysis

First of all, results of **examinations results used for standard of reference** will be presented: at subject level showing number and frequency of AFP results by category ($>200\text{ng/mL}$ or $\leq200\text{ng/mL}$) and by number of nodules for a subject (multiple or single nodule), previous contrast enhanced imaging modalities (CT and/or MRI), timelines and type of contrast agent category for MRI. At nodule level, typical imaging hallmark obtained by nodule (CT and/or MRI) and intensity of parenchyma relative to the nodule at each available phase will be presented. Timelines for biopsy (or surgical specimen collection) will be presented at subject level and nodules histology results (HCC, other malignant, regenerative or dysplastic nodule, benign, uncertain) will be presented at nodule level.

P03277 imaging diagnosis (HCC and not HCC) will be presented at nodule level displaying number and frequency for each standard of reference group HCC or not HCC according to the **Table 2**.

Table 2 : Diagnostic value evaluation for HCC

		P03277 imaging expert reading results			
		HCC: (Typical features on this MR examination)	Not HCC (No nodule/atypical features)		
Standard of reference	HCC:	True positive $n1$	False negative $n3$	Total $n1+n3$	
	Not HCC including uncertain cases	False positive $n2$	True negative $n4$	Total $n2+n4$	
		Total $n1+n2$	Total $n3+n4$	All total $N+$	

The following parameters will be calculated:

Sensitivity: the number of nodules showing true positive HCC divided by all nodules considered HCC according to standard of reference ($n1 / n1+n3$)

Specificity: the number of nodules showing true negative HCC divided by all nodules considered as not HCC or uncertain as standard of reference ($n4 / n2+n4$)

Accuracy: the number of nodules showing true positive HCC and true negative HCC over all nodules ($n1+n4 / N+$)

Positive predictive value: the number of nodules showing true positive HCC /all nodules showing HCC according to P03277 imaging ($n1 / n1+n2$)

Negative predictive value: the number of nodules showing true negative HCC /all nodules not showing HCC according to P03277 imaging ($n4 / n3+n4$)

 CONFIDENTIAL	Protocol No. GDX-44-008 Version No.4.0 including amendments 1 and 2 12 December 2017	Page 51 / 64

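### Already-confirmed HCC nodules are eligible and pooled into one sensitivity per dose, so the result depends on case mix that the suspected-nodule objective does not acknowledge

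*Protocol*

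**What the plan says.** Protocol section 4.1, criterion 5 (same wording in the synopsis), admits subjects with one to three untreated nodules of at most 3 cm seen on enhanced CT or MRI, "confirmed for HCC or not". There is no cap or stratum for confirmed cases. Section 2.1 sets the objective "in patients with suspected small nodules and chronic liver disease". Section 8 describes the 30 subjects of the first cohort as having suspected nodules, around 66% of them with HCC. Section 1 places the hoped-for gain in atypical lesions: "Some small HCC usually showing atypical features may be better seen and characterized under imaging with P03277".

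Under section 7.1 a nodule is HCC on P03277 when it has arterial hypervascularization with portal or delayed wash-out. The reference standard calls a nodule HCC by any of three routes:

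- positive histology;
- a nodule "characterized by typical features using two different triphasic contrast enhanced modalities", where the typical features are the same two;
- AFP above 200 ng/mL with a single nodule.

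Histology may precede the study MRI: section 9.1.4 says "it is acceptable to record results from histology done within 2 months prior to P03277 administration".

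Section 12.3 defines sensitivity as "the number of nodules showing true positive HCC divided by all nodules considered HCC according to standard of reference" and presents efficacy by dose. It tabulates prior hallmark and histology by nodule and AFP by subject, but does not cross any of them with the P03277 result.

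**The concern.** The objective concerns suspected nodules and the rationale singles out small atypical HCC. The sensitivity that section 12.3 prescribes mixes these with nodules whose diagnosis was settled before P03277 was given. Where it was settled by the imaging hallmark, the nodule has already shown the feature on which P03277 will be scored, and it says little about atypical lesions.

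Two things are at stake. The pooled figure cannot be read as performance in the lesions the rationale targets. And because the 30-subject and 10-subject cohorts are enrolled one after the other without randomisation, nothing balances the share of confirmed nodules, so sensitivities shown by dose can differ for that reason only.

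**Working it through.** **The plan's own figures.** Section 8 gives 30 and 10 subjects and about 66% HCC in the first cohort. That is 0.66 × 30 = 19.8, about 20 HCC subjects. If the same share held in the second cohort (an assumption), 0.66 × 10 = 6.6, about 7. The protocol states no precision target and plans no test, so there is no power figure to reproduce.

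**Inputs not in the documents.** The share f of reference-HCC nodules confirmed at entry, and the sensitivities Se_c (confirmed) and Se_u (not yet confirmed), are assumed below.

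**Formula.** Pooled sensitivity = f × Se_c + (1 − f) × Se_u. The shift from Se_u is f × (Se_c − Se_u).

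**Confirmation by imaging hallmark** (Se_c above Se_u expected):

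| Se_c, Se_u | f = 0.25 | f = 0.50 | f = 0.75 |
|---|---|---|---|
| 0.95, 0.60 | 0.688 | 0.775 | 0.863 |
| 0.90, 0.70 | 0.750 | 0.800 | 0.850 |

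For example, 0.25 × 0.95 + 0.75 × 0.60 = 0.2375 + 0.45 = 0.6875. Two doses with identical performance in each type of nodule, one with f = 0.25 and the other with f = 0.75, would differ by 86.25 − 68.75 = 17.5 points in the first row and 10 points in the second. Over a wider grid (Se_c 0.90 to 1.00, Se_u 0.50 to 0.82) the upward shift runs from 0.25 × (0.90 − 0.82) = 2.0 points to 0.75 × (1.00 − 0.50) = 37.5 points.

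**Confirmation by histology or AFP** (no hallmark required). With Se_c = 0.60 and Se_u = 0.80, the pooled value is 0.75, 0.70 or 0.65, a shift of −5, −10 or −15 points. With Se_c = Se_u = 0.80 the shift is zero. The direction therefore depends on the route of confirmation.

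**What can be split.** A nodule that meets any of the three routes before P03277 is reference HCC. In Table 2 restricted to such nodules, n2 = n4 = 0. Specificity n4/(n2+n4) is 0/0, PPV n1/(n1+n2) is 1 by construction if any nodule is called HCC, NPV n4/(n3+n4) is 0 or undefined, and accuracy equals sensitivity. Only sensitivity carries information there.

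**How a not-yet-confirmed nodule becomes reference HCC.** The reference uses previous imaging, the most recent AFP and histology, and the Day+1 diagnosis excludes P03277 images (section 9.1.3). If none of the routes is met before P03277, essentially only histology at the optional Visit 4 remains. That denominator is small and selected by who is biopsied or resected.

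**Precision.** With 20 HCC nodules, 16/20 = 0.80 has an exact 95% CI of 0.56 to 0.94. With 10, 8/10 has 0.44 to 0.97.

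**The case against.** The strongest reply is that the protocol is open about its scope. Criterion 5 states it outright, and suspected nodules is used for enrolled nodules generally, for instance in non-inclusion criterion 11 and section 9.1.1. Objective 2.1 does not say undiagnosed, and the sentence on atypical HCC is a hope in the rationale. The study is exploratory, plans no test or formal dose comparison, and acknowledges its small size. Section 12.3 already shows the case mix, and the analysis plan, not at hand, may hold further breakdowns.

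Much of this stands. The mismatch is one of wording and interpretation, and no error rate or power is affected. But the protocol itself fixes the pooled sensitivity per dose, and separate tables of hallmark, histology and AFP do not show how the P03277 result varies with them.

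Three stronger readings are tempting, and the documents do not support them:

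- A reader might infer that pooling inflates sensitivity as such. Histology and AFP confirmation do not require the hallmark, so the effect can be nil or downward.
- A reader might want the whole of Table 2 split by confirmation status. The confirmed stratum has no reference-negative nodules, so four of the five measures are empty or trivial there.
- A reader might take the not-confirmed stratum as the answer to objective 2.1. It rests on optional later histology and is itself a selected group. Nor would setting confirmed nodules aside remove the overlap between the imaging route of the reference and the P03277 reading.

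**Conclusion.** The point holds in limited form. Eligibility is wider than the wording of 2.1, section 1 and section 8, and the single sensitivity per dose depends on how many nodules were already confirmed and by which route. An upward effect is expected for hallmark-confirmed nodules only. The size cannot be taken from the documents: every shift shown rests on assumed confirmed shares and assumed sensitivities. They show that a case-mix difference of 10 to 17.5 points between equally performing doses is possible, not that it will occur. The consequence is for interpretation of a descriptive study, and the remedy is cheap.

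**What to change.** Keep eligibility and the pooled Table 2. In section 12.3 add one table, by dose, of sensitivity among reference-HCC nodules, split (a) by whether the typical hallmark was already present on prior CT/MRI and (b) by reference route: two-modality imaging, histology before P03277, histology after P03277, AFP. State how a nodule qualifying by more than one route is classed. Do not split specificity, PPV, NPV or accuracy for the confirmed stratum, and do not present the not-confirmed stratum as the sole answer to 2.1. State in 2.1 and section 8 that already-confirmed HCC is included.

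No new data are needed: sections 9.1.1 and 9.1.4 already collect hallmark, modality, AFP and histology with dates. The cost is an extra descriptive table whose strata will be small and whose intervals will be wide, most of all in the 10-subject cohort.

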4.2 Non Inclusion Criteria

1. Pregnant or breast-feeding female subject (a female subject of childbearing potential or with amenorrhea for less than 12 months must have a negative urine or serum pregnancy test and within 24 hours prior to study MRI).
2. Subject presenting with hepatic nodule more than 3 cm in addition to nodule(s) less than or equal to 3 cm
3. Subject already treated for HCC by surgery or thermal ablation for which the resection or coagulation area is less than 2cm from the new nodule(s)
4. Subject previously treated by transarterial chemoembolization
5. Subject with moderate or severe renal impairment (eGFR < 60 mL/min/1.73m²) based on measurement done or available within the 7 days before P03277 administration and assessed after any iodinated contrast agent administration, or with dialysis end stage renal disease (ESRD)
6. Subject with known class III/IV congestive heart failure according to the New York Heart Association classification

 CONFIDENTIAL	Protocol No. GDX-44-008 Version No.4.0 including amendments 1 and 2 12 December 2017	Page 27 / 64
---	--	--------------

7. Subject having received or is scheduled to receive any contrast agent within 7 days before P03277 planned administration date and within 3 days after P03277 planned administration date.
8. Subject with known contra-indication(s) to the use or with known sensitivity to drugs from a similar pharmaceutical class as P03277
9. Subject having received any investigational medicinal product within 7 days prior to P03277 planned administration date
10. Subject presenting with any contraindication to MRI examination (see recommendations of the French Society of Radiology)
11. Subject having planned palliative/treatment interventions for the suspected nodules (radiotherapy, chemotherapy or others) during the study period except for biopsy/surgery
12. Subject related to the investigator or any other study staff or relative directly involved in the study conduct
13. Subject previously enrolled in this study
14. Subject with anticipated, current or past condition (medical, psychological, social or geographical) that would compromise the subject's safety or her/his ability to participate in the study.
15. Subject unlikely to comply with the protocol (e.g., uncooperative attitude, inability to return for follow-up visits and/or unlikelihood of completing the study).
16. Vulnerable subject according to article L1121-6 of the French Public Health Code,
17. Subject under guardianship or unable to give his/her consent according to the article L1121-8 of the French Public Health Code

Subjects presenting with one or more of these non-inclusion criteria must not be selected and included in the study.

